Consent and baseline assessment will be conducted by staff employed by Barnardo's they will be conducted in a safe, therapeutic and convenient location for the young person, this will include facilities managed by Barnardo's, community facilities accessed as part of community partnerships, children's services, school and the young person's home. Data will be collected on-line, and randomisation will be conducted independent of Barnardo's by research staff after baseline data collection has been conducted.

Inclusion criteria

- 1. Young people aged 13-17 years inclusive who are resident in the Bristol or Newport LA.
- 2. Currently involved with the police or youth justice service or at risk of offending.

At risk of offending defined as having at least one of the following risk factors, assessed on referral.

- Previously being in the secure estate.
- Currently, or previously, persistently absent from school (defined by DfE as 10% or more).
- Have been the victim of violence.
- Currently, or have attended alternative education provision.
- Received multiple suspensions from school or has been permanently excluded.
- Have a sibling or parent who has been involved in serious violence or identified as facing exploitation harm.
- Currently, or have been, in the care system.
- Have been identified as being at risk of criminal exploitation.
- Currently or have had a social worker.
- Have previously been in contact with youth justice services.
- Have been arrested, admitted an offence and released by the police with no further action.
- 3. Evidence of alcohol or substance use on at least 4 occasions in the past 28 days, assessed using a single substance use frequency question on referral to Barnardo's.
- 4. Willing and able to provide informed consent or willing to provide assent with a parent/ carer willing to provide consent.

Exclusion criteria:

- 1. Alcohol or substance severity that requires inpatient residential treatment or immediate detoxification.
- 2. Severe mental health condition requiring immediate psychiatric assessment.

Figure 3: Flow chart of recruitment processes.

Referral partners identify young people who would be suitable for MDFT

Referral partners share information with Barnardo's through secure referral form.

Barnardo's contacts young person to assess frequency of substance use, check eligibility, and gauge interest, share information sheet and privacy notice

If willing to take part young person attends for baseline assessment

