estimates found in systematic reviews of MDFT (Filges T. et al., 2018, van der Pol et al., 2017b). This equates to a number needed to treat of 6, where at least one in six participants receiving MDFT would show clinically important benefits, and a difference in the frequency of substance use of at least 13% in the MDFT group. Detecting an effect size smaller than this provides no additional benefit, the commissioning of services in England and Wales requires the service to achieve a clinically important difference for the target population. To detect this difference, with power at 80% and alpha of 0.05 and a two-tailed test, requires a sample of 480 participants followed-up at the 6-month endpoint. Using data from other studies of substance using adolescents (Coulton S et al., 2023, Deluca et al., 2020) we estimate the prepost-test correlation of the frequency of substance use to be 0.4, and incorporating this into the sample size calculation reduces the number followed-up to 364, 182 in each group. Assuming a loss to follow-up at the endpoint of 10%, similar to other studies in adolescent substance use populations (Coulton et al., 2024) inflates the number needed to randomise to 400. Assuming 80% of those eligible will be willing to consent an indication of acceptability of the study to participants and a lower figure than other studies in similar populations (Coulton et al., 2024) would mean we would need to approach 480 across both sites. Recruitment will be continuous between September 2025 and January 2027, 28 per month will need to be approached in total across both sites per month with the expectation that 24 will consent to participate in the trial across both sites. We anticipate. Based on relative population size that 40% of referrals will come from Newport and 60% from Bristol.

Table 2: Recruitment/ retention table

	Q1	Q2	Q3	Q4	Q5	Q6	Q7	Q8	Q9	Q10	Q11
Months (e.g. Oct-Dec 23):	May-Jul 25	Aug-Oct 25	Nov 25 - Jan 26	Feb - Apr 26	May-Jul 26	Aug-Oct 26	Nov 26 - Jan 27	Feb - Apr 27	May-Jul 27	Aug-Oct 27	Nov 27 - Jan 28
Target number of children and young people referred into the project	0	50	75	75	75	75	75	75	218	360	500
Target number of children and young people recruited to the project and evaluation	0	40	60	60	60	60	60	60	174	288	400
Target number of children and young people who withdraw/drop out	0	4	6	6	6	6	6	6	23	35	40

Table 3: Sample size calculations

		PARAMETER		
Minimum Detectable Effect Size (MDES)		0.27		

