Pre-test/ post-test	level 1 (participant)	0.40		
correlations	level 2 (cluster)	n/a		
Alpha ²		0.05		
Power		0.8		
One-sided or two-sided?		2-sided		
	Intervention	182		
Number of participants	Control	182		
	Total	364		

Outcome measures

To ensure outcomes are accessible to a wide range of potential participants we will make outcomes available in other languages, where validated and provide translators for other languages. As we anticipate a higher level of intellectual disability than the general population, we will seek the advice from the Tizard centre at the University of Kent who are specialists in the conduct of research with people with intellectual disabilities. We will seek advice on how outcomes can be presented to meet the needs of the target population; this will include using different fonts, colours, and the restriction on the amount of text presented on each page. The completion of outcomes will be supported with research staff available to address any questions. All outcome tools will be agreed with our youth advisory panel prior to use.

² Please adjust as necessary for trials with multiple primary outcomes, 3-arm trials, etc., when a Bonferroni correction is used to account for family-wise errors.

Baseline measures

Key demographic variables will be collected at baseline, these include DoB, sex, ethnicity, and index of material deprivation (IMD) derived from the participants postcode and converted to IMD using the IMD lookup tool:

https://geoconvert.ukdataservice.ac.uk/help/faq.html.

The severity of substance use, for stratification, will be determined by Global Assessment of Individual Need short screener for substance use (GAIN-SS; (Dennis et al., 2006)). This 5-item self-completed questionnaire has high sensitivity, 0.86, and specificity, 0.93, with an area under the curve of 0.97, in identifying adolescents who meet DSMIV criteria for low/moderate or severe substance use disorders. This outcome will be used as a stratification variable in the randomisation to ensure both groups have a similar distribution of low/moderate and severe cases.

Primary outcome

While the study will collect secondary outcomes on offending behaviour and delinquency, it is important to note the heterogeneity of the population is such that some participants will not be engaging in offending while all will have used substances. The proposed primary outcome for the study is frequency of substance use over a given period.

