Fractional regression analysis will be performed to model the relationship between prerandomisation factors, and demographics on observed outcomes at 6 months, for the primary outcome. Interaction terms with allocation arm will be included in the analysis, and a significance level of 0.1 will be used to determine which factors are to be included in the model. Pre-randomisation factors will include ethnicity, sex, age, IMD decile, severity of substance use, and baseline family cohesion, motivation, self-efficacy and expectancy. This analysis will be augmented by an additional analysis including participants in the intervention arm only using the same pre-randomisation factors but also including process measures of adherence, intervention fidelity, and therapeutic alliance.

Latent class approaches will be used to explore the hypothesised mechanism of change exploring changes over time in family cohesion, motivation to change, self-efficacy and substance use expectancy.

Qualitative analysis

The aim of the qualitative analysis in the efficacy study will be to link samples by grouping, comparing, and contrasting responses from all data sources to address the research questions. This linking of data allows for a concentrated and more meaningful analysis of the influence of the programme through its contexts and mechanisms, and of its perceived impact through a thematic blending of data elements. The key questions that we will seek to answer at this stage will include:

- Are there any residual or new external or logistical issues impacting referral, intervention delivery, or attrition?
- What are young peoples' positive and negative experiences of the intervention and how do these fit with providers' perceptions?
- At what points in the intervention have these experiences occurred?
- Are there practices associated with the intervention that can be amended to further increase its acceptability and impact?
- Do stakeholders see the intervention as impacting participant's behaviour?
- In what ways has substance use and offending been impacted?

This provides an opportunity to explore the perceptions of the intervention from the point of view of a variety of stakeholders using Normalisation Process theory (NPT; (Finch et al., 2012). Bracketing, reflexivity, and member checking will be employed to ensure trustworthiness and rigour.

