Using NPT, the objectives of the qualitative analysis will be to identify useful and unnecessary elements of the intervention, explore planning and implementation issues, understand issues around ethnicity and equity, and identify perceived barriers or facilitators of implementation in usual practice. Taking an inductive and deductive approach, no existing theory will be used to facilitate the coding, which will allow for findings to emerge naturally from the data. Findings will be mapped onto NPT to elucidate coherence (the extent to which the intervention makes sense to those involved in its implementation), cognitive participation (the extent to which individuals involved in implementing the intervention are motivated to engage with it), collective action (the extent to which the intervention is incorporated into everyday practice and is implemented consistently and reliably), and reflexive monitoring (the extent to which the intervention is evaluated and reviewed over time to ensure it remains relevant and effective).

Sub-group analyses

Sub-group analyses by their nature tend to be under-powered. To maintain power in the analysis we will use latent-class cluster analysis to explore the emergence of different clusters

who might experience differential effects. Latent class analysis will explore the potential effect of ethnicity, age, sex, socio-economic status, criminal involvement and severity of substance use on the effects observed for the primary outcome.

Longitudinal follow-ups

Participant data will be collected at baseline, prior to randomisation and again at 6- and 12-months post randomisation. Our primary endpoint will be the 6-month post-randomisation date. Core outcomes and the time of data collection are presented in table 4.

Implementation and process evaluation

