An aspect of our qualitative work with key stakeholders involves examining participants' positive and negative experiences of the referral process and intervention, exploring how these perspectives concur with those who deliver the intervention, explore at what points negative and positive experiences are at their greatest and what steps could be taken to ameliorate these experiences to improve the delivery and acceptability of the intervention.

Exploring Adaptation

The mechanism of change will be explored using a latent class mediation model. Exploring factors that impact on the mechanism of change will be assess the relationship between prerandomisation factors and observed outcomes at 6 months. Pre-randomisation factors include sex, age, ethnicity, IMD decile, family cohesion, motivation to change, self-efficacy and substance use expectancy.

In addition to quantitatively understanding the mechanism of action, the qualitative analysis will provide an opportunity to explore the perceptions of the intervention from the point of view of a variety of stakeholders. The analysis will allow us to explore what elements of the interventions are useful and what elements are unnecessary, issues around how the interventions are planned and implemented and the perceived barriers or facilitators of implementation in usual practice.

Through a detailed exploration of the key dimensions, we plan on stating our logic model at the start of the project, and revise this again at the end of the internal pilot stage. The logic model will incorporate the qualitative research exploring stakeholder perceptions of acceptability and usefulness, hindrances and facilitators associated with the process and intervention but will also combine quantitative analysis exploring adherence, dosage, fidelity, and mediators associated with behaviour change. This mixed methods synthesis will enable

us to understand what works, how it works, when it works and for whom it works and provide a detailed elaboration of the mechanisms and processes through which it works.

Exploring Factors Affecting Implementation

Interviews with intervention delivery partners and key stakeholders, including those delivering similar substance use services to CYP, will explore how sustainable the intervention is in its current format. What key challenges were experienced and what changes might be necessary to roll out the intervention more widely.

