We will ensure participants do not feel coerced to consent. Once a participant is referred to the service any consent to participate in the trial is theirs solely to make. Not consenting to the research will not impact on the BAU they receive, and this will be explained verbally and in writing. If a participant does consent it will be made clear that they can withdraw consent at any time.

We will minimise the potential for participants and staff to experience any adverse or iatrogenic events. In our experience of conducting similar studies in similar populations the risk of adverse events is low, as is the risk of iatrogenic events. We will implement a standard operating procedure for the reporting of adverse events that involves an independent

experienced third-party making recommendations on the severity of any event and whether they are associated with the trial. All staff involved in the study will have enhanced DBS accreditation and will be familiarised with safeguarding practice and procedures.

University of Kent Social Research Ethics Identifier: SRE 1200

Barnardo's Research Ethics Committee Identifier: BREC (23)

Trial Registration: ISRCTN10024151

Data protection

All systems and personnel are approved for the management of clinical and sensitive data and are ISO certified to ISO27001 standard. This includes all physical systems, systems to detect intrusion, encryption of data from point of collection to storage, quality assurance and audit trails associated with any data collected. All identifiable data collected will be done with explicit consent and limited to data to allow participants to be contacted for follow-up. Data linkage will employ a unique identifier where the link to identifiable information will be stored on an encrypted secure database. Researchers will be trained to GCP standard and will comply with all relevant data protection legislation. Once final follow-up is completed, personally identifiable information will be deleted from the dataset held by the university and where consent to the trial has been granted encrypted data will be transferred to the Youth Endowment Fund data archive. Consent for transfer of data will be taken from those resident in England, and data used by DfE, name, DoB and postcode will be transferred. Data collection and management will be governed by a trial specific Standard Operating Procedure agreed and approved by ethics.

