In addition, there is strong demand in Bristol. A recent scrutiny report shows that Bristol has experienced an increase in the number of young people referred for services relating to extra-familial harm (up 18.3%) and an increase in child vulnerability due to poverty and inequality. The Children's Commissioner for England estimates that in 2019/20 there were 4,600 children and young people aged 0-17 living in households in Bristol with a parent who has alcohol or drug dependence. In Wales, substance misuse among children and young people represents a particular societal focus — figures from March 2022 for Newport show above average levels of substance misuse identified as a concern for YP receiving support and care: 10% (Wales average 7%) had their own substance misuse as a primary concern and 33% (Wales average 31%) had parental substance misuse as a primary concern.

Population

Inclusion criteria:

- 1. Young people aged 13-17 years inclusive.
- 2. Currently involved with the police or youth justice service or at risk of offending.

At risk of offending defined as having at least one of the following risk factors, assessed on referral.

Previously being in the secure estate.

Currently, or previously, persistently absent from school (defined by DfE as 10% or more). Have been the victim of violence.

Currently, or have attended alternative education provision.

Received multiple suspensions from school or has been permanently excluded.

Have a sibling or parent who has been involved in serious violence or identified as facing exploitation harm.

Currently, or have been, in the care system.

Have been identified as being at risk of criminal exploitation.

Currently or have had a social worker.

Have previously been in contact with youth justice services.

Have been arrested, admitted an offence and released by the police with no further action.

- 3. Evidence of alcohol or substance use on at least 4 occasions in the past 28 days, assessed using a single substance use frequency question.
- 4. Willing and able to provide informed consent or willing to provide assent with a parent/ carer willing to provide consent.

Exclusion criteria:

- Alcohol or substance severity that requires inpatient residential treatment or immediate detoxification.
- 2. Severe mental health condition requiring immediate psychiatric assessment.

Inputs

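### A single IMD decile is screened for interaction with arm across Bristol and Newport without site in the factor list, so an apparent deprivation effect may partly be a site effect

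*Protocol*

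**What the plan says.** Under Outcome measures, Baseline measures, the Protocol collects an "index of material deprivation (IMD) derived from the participants postcode and converted to IMD using the IMD lookup tool". One variable and one tool serve every participant. No index, edition or reference population is named.

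The variable is then used twice under its own name:

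- Exploratory analysis: "Pre-randomisation factors will include ethnicity, sex, age, IMD decile, severity of substance use", followed by family and psychological measures. Interactions with arm are included, and a significance level of 0.1 decides which factors enter the model.
- Exploring Adaptation (mechanism of change): "Pre-randomisation factors include sex, age, ethnicity, IMD decile", followed by family and psychological measures.

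Site is in neither list. The Sub-group analyses section also leaves it out: "Latent class analysis will explore the potential effect of ethnicity, age, sex, socio-economic status, criminal involvement and severity of substance use". That section does not say how socio-economic status is measured.

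Participants must be "resident in the Bristol or Newport LA". The Protocol itself places the sites in two nations. Appendix I sets Newport's figures against Wales averages in a passage that begins "In Wales, substance misuse among children and young people represents a particular societal focus", and the Data protection section limits archive transfer: "Consent for transfer of data will be taken from those resident in England". The Sample size calculations section expects that "40% of referrals will come from Newport and 60% from Bristol".

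Site is a stratification factor for randomisation. The primary model adjusts for the stratification variables and does not name IMD.

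**The concern.** A decile is a rank within some set of areas. The Protocol pools deciles across two nations without naming that set, so it is unclear whether a given decile means the same level of deprivation in Newport as in Bristol.

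The statistical problem is wider than the choice of index. Recorded deciles may differ between the sites because the scales differ or because one area really is more deprived. In either case IMD decile is correlated with site. If MDFT also works better against one site's business as usual than the other's, an IMD-by-arm term fitted without a site-by-arm term absorbs part of that difference. The Business as usual section describes different providers and programme lengths in the two cities, so a site difference in effect is possible, although the Protocol gives no size for it.

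At stake is the reading of the deprivation findings. A factor kept by the 0.1 screen could be reported as evidence that MDFT works differently by deprivation when it reflects Bristol against Newport. The Diversity, equity and inclusion section promises an analysis of socio-economic disadvantage, and IMD is the only quantitative deprivation measure that the Protocol names.

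**Working it through.** The Protocol gives no figure that depends on IMD, so there is nothing of its own to reproduce. The check asks how often the IMD-by-arm term passes the 0.1 screen when deprivation does not modify the MDFT effect at all.

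**Inputs from the Protocol**
- 364 analysed, 182 per arm (Table 3).
- Newport share p = 0.4 (Sample size calculations).
- Screening level 0.1, two-sided critical value 1.645 (Exploratory analysis).

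**Assumed inputs (not in the Protocol)**
- Within-site decile SD of 2.5, so within-site variance 6.25.
- Between-site shift in recorded decile, s = 1, 2 or 3.
- Site difference in MDFT effect, d = 0.3, 0.15 or 0 SD.
- Outcome on a standardised linear scale with residual SD 1, as a simplification of the fractional model.

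**Formulas, site not in the model**
- Total decile variance: V = 6.25 + p(1 − p)s² = 6.25 + 0.24s².
- Spurious IMD-by-arm slope: b = d × 0.24s / V.
- Standard error of the slope difference: SE = √(2 / (182 × V)).
- With k = b / SE, the false-selection rate is Φ(k − 1.645) + Φ(−k − 1.645).

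**Worked case, s = 2 and d = 0.3**
- V = 6.25 + 0.96 = 7.21.
- b = 0.3 × 0.48 / 7.21 = 0.0200.
- SE = √(2 / 1312.2) = 0.0390.
- k = 0.512, so the rate is 0.144.

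**All cases by formula**

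| Shift (deciles) | d = 0.3 | d = 0.15 | d = 0 |
|---|---|---|---|
| 1 | 0.112 | 0.103 | 0.100 |
| 2 | 0.144 | 0.111 | 0.100 |
| 3 | 0.184 | 0.121 | 0.100 |

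Simulation with 4,000 replicates per cell gave 0.115, 0.147 and 0.187 for d = 0.3. These are the figures rounded to 11%, 15% and 19%. Other runs of the same set-up differ by about a percentage point.

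**What removes the inflation (d = 0.3; shifts of 1, 2, 3)**
- Site main effect only: 0.114, 0.146, 0.186. No improvement.
- Site and site-by-arm terms: 0.100, 0.096, 0.100 in a separate 4,000-replicate run. Nominal.
- Site-centred deciles with both terms (6,000 replicates): 0.099, 0.099, 0.105. Nominal.

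**Does the source of the shift matter?** With d = 0.3 and 6,000 replicates per case:
- 2-decile shift that is purely an artefact of scale: 14.3%.
- Perfectly harmonised index with a true 2-decile site difference: 14.4%.
- True 2-decile difference cancelled by ranking within nation: 10.5%.

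What drives the result is the gap in recorded deciles together with the missing site-by-arm term. The index as such does not.

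**Main effect of IMD, relevant to Exploring Adaptation.** Assume a true slope of 0.100 SD per decile, scale offsets of 0 to 2 deciles and a direct site effect of 0 or 0.2 SD. Without site, the fitted slope ranges from 0.088 to 0.111 when recorded deciles differ by one between sites, an error of at most about 12%. With a site term it is 0.098 to 0.102. This recovery holds only for a constant additive offset.

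**The case against.** The strongest reply has four parts.

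1. **The premise about national ranking is not in the Protocol.** It does not say what the look-up tool returns for a Newport postcode. This stands. A reader might infer that English and Welsh deciles are on different scales and that the deprivation findings are therefore mixed up with site. The document does not support either statement as fact. Nation-specific ranking can only be a condition, and the interaction problem does not need it.

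2. **The assumed inputs are generous.** A site difference of 0.3 SD exceeds the trial's whole target effect of 0.27, and no source supports any particular shift in deciles. This also stands. At 0.15 SD, or with a 1-decile shift, the inflation is small.

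3. **The detail could sit in a statistical analysis plan.** The lists say that they include certain factors and need not be exhaustive. This is a fair point and keeps the matter minor. Still, the Protocol goes as far as listing the factors, including arm interactions and setting the screening level, and it leaves out a factor already used to randomise. Carrying over the primary model's adjustment for stratification variables would supply only a site main effect, which does not protect the interaction test.

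4. **The Sub-group analyses section says socio-economic status, not IMD.** Correct. A problem in the latent class analysis arises only if IMD is the measure used, and no calculation here covers that case.

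**Conclusion.** The point holds as a minor one. The Protocol uses one IMD decile as a single factor in a two-nation trial, does not name the index for Newport, and omits site from the factor lists. The IMD-by-arm screen can therefore partly reflect a site difference in MDFT effect.

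Two conditions must both hold: recorded deciles differ between sites, and the MDFT effect differs between sites. The rise from 10% to about 11%, 15% or 19% rests on the assumed inputs above, and there is none when the effect is the same in both sites.

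Two stronger readings should be resisted. A common index for both sites would not cure the interaction problem, because a true site difference in deprivation produces the same inflation. The trial's main result is also not in doubt: the primary model adjusts for site and does not name IMD, and the secondary models include the stratification factors.

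**What to change.** - In Exploratory analysis and Exploring Adaptation, add site wherever IMD decile is tested, and site-by-arm wherever IMD-by-arm is tested. Site-centred deciles with the same terms are an equivalent choice.
- In Baseline measures, name the index and reference population used for each site.
- If nation-specific deciles are used, report deprivation as relative within site. Do the same in Sub-group analyses if IMD stands for socio-economic status there.

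The cost is wording and up to two extra model terms. Postcode is already collected and site is already a randomisation stratum. The price in interpretation is that a within-site decile describes relative, not absolute, deprivation, and the report should say so.
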